10.5.4 Slit Lamp Biomicroscopy

Biomicroscopy will be performed in each eye at each visit, by slit lamp examination, without pupil dilation, including but not limited to eyelids/lashes, conjunctiva, cornea, and anterior chamber. Observations for the examination will be graded on a 5-point scale (0 = none, 0.5 = trace, 1 = mild, 2 = moderate, 3 = severe) except for the anterior chamber (in cells: 0 = 0 cells, + 0.5 = 1 - 5 cells, + 1 = 6 - 15 cells, + 2 = 16 - 25 cells, + 3 = 26 - 50 cells, and + 4 = > 50 cells; in flare: 0 = none, + 1 = faint, + 2 = moderate, + 3 = marked and + 4 = intense).

The number and percentage of subjects with clinically significant biomicroscopy findings will be tabulated by PT, assessment timepoint and treatment group. A clinically significant finding is defined as more than one severity grade increase (worsening) from baseline, or a positive status change from absence at baseline to presence at postbaseline (not associated with a severity grade) in one or both eyes. If a pathology is recorded at a follow-up visit but not at baseline, the baseline will be imputed with the same pathology, with a grade of zero (none).

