Superficial Punctate Keratopathy

0	=	No superficial punctate keratopathy
+0.5	=	Trace
+1	=	Mild
+2	=	Moderate
+3	=	Severe

Note: Punctate epithelial staining, Filaments, Infiltrates, Edema, Cornea Guttae, Endothelial Pigment, Keratic Precipitates, Neovascularization, Opacity(ies), Stromal Haze are graded 0, +0.5, +1, +2, +3.

Anterior Chamber:

Cells, Flare, Anterior Synechiae, Hypopyon, Hyphema will be graded as 0, +0.5, +1, +2, +3, +4.

Iris/Pupil:

Rubeosis Iridis, anterior chamber angle involved, Rubeosis Iridis, anterior chamber not involved, Afferent Pupillary Defect, Posterior Synechiae, Transillumination Defects, Pseudoexfoliative Material, Peripheral Iridectomy, Laser Peripheral Iridotomy will be evaluated with no grading.

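### The slit-lamp table in SAP 10.5.4 omits new low-grade hypopyon, hyphema and similar graded signs, and leaves the unit of a grade undefined

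*SAP*

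**What the plan says.** SAP 10.5.4 plans one output for biomicroscopy: "The number and percentage of subjects with clinically significant biomicroscopy findings will be tabulated by PT, assessment timepoint and treatment group". A finding qualifies by one of two routes.

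- Graded findings: "A clinically significant finding is defined as more than one severity grade increase (worsening) from baseline".
- Ungraded findings: "or a positive status change from absence at baseline to presence at postbaseline (not associated with a severity grade) in one or both eyes".

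A pathology first recorded at follow-up is given a baseline grade of zero. A new graded sign is therefore judged under the first route, as a move from 0 to its recorded grade.

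Most structures are "graded on a 5-point scale (0 = none, 0.5 = trace, 1 = mild, 2 = moderate, 3 = severe) except for the anterior chamber". For the anterior chamber the SAP gives scales for cells (0, +0.5, +1, +2, +3, +4) and for flare: "in flare: 0 = none, + 1 = faint, + 2 = moderate, + 3 = marked and + 4 = intense". It gives none for hypopyon, hyphema or anterior synechiae.

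The sites work from section 3.18 of the Operations Manual (Protocol Appendix F). For the anterior chamber it says "Cells, Flare, Anterior Synechiae, Hypopyon, Hyphema will be graded as 0, +0.5, +1, +2, +3, +4". For the cornea, a note that also covers infiltrates ends "Keratic Precipitates, Neovascularization, Opacity(ies), Stromal Haze are graded 0, +0.5, +1, +2, +3". Only the iris and pupil findings, among them posterior synechiae and transillumination defects, are recorded without a grade.

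**The concern.** Biomicroscopy is a named safety measurement (Protocol 3.6, SAP 3.4). The visit lists in Operations Manual 2.1 place it at Hours 0, 1 and 7 of every treatment visit. The SAP reports it through a single thresholded table, with no slit-lamp listing and no shift table, although SAP 10.5.5 and 10.5.6 do list manifest refraction and fundoscopy.

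Three features of the rule can affect that table.

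1. Signs that matter on any appearance, such as hypopyon, are graded by the sites. They fall outside the absence-to-presence route and must clear the grade threshold.
2. The grades are unevenly spaced, so more than one grade can mean more than one scale step or more than 1.0 point. Two programmers following the SAP could produce different tables.
3. The flare scale in the SAP is not the one given to the sites.

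At stake is whether the table can be read as a complete account of slit-lamp worsening in each arm.

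**Working it through.** The plan states no figure here, so the check is to list every possible worsening and apply the rule under both readings.

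**Inputs.** The general scale is 0, 0.5, 1, 2, 3 (SAP 10.5.4). The anterior chamber scale in the manual is 0, 0.5, 1, 2, 3, 4 (Operations Manual 3.18). The SAP flare scale is 0, 1, 2, 3, 4 (SAP 10.5.4).

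**Rules.** Steps reading: the finding moves up more than one position on the scale. Points reading: follow-up grade minus baseline grade is greater than 1.0.

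**Counts.** A scale with k levels has k(k − 1)/2 possible worsenings. Of these, k − 1 are moves to the next level and fail the steps reading. No such move exceeds 1.0 point, so they fail the points reading too. On scales with a 0.5 level, 0 to 1 is two steps but exactly 1.0 point, so it passes by steps and fails by points.

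| Scale | Possible worsenings | Count by steps | Count by points | Count on neither |
|---|---|---|---|---|
| 0/0.5/1/2/3 | 5×4/2 = 10 | 10 − 4 = 6 | 6 − 1 = 5 | 4 |
| 0/0.5/1/2/3/4 | 6×5/2 = 15 | 15 − 5 = 10 | 10 − 1 = 9 | 5 |
| 0/1/2/3/4 (SAP flare) | 5×4/2 = 10 | 10 − 4 = 6 | 6 | 4 |

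On the general scale the four that never count are 0 to 0.5, 0.5 to 1, 1 to 2 (mild to moderate) and 2 to 3 (moderate to severe). The manual's anterior chamber scale adds 3 to 4.

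**New graded signs (baseline 0).**

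| New grade | By steps | By points |
|---|---|---|
| +0.5 | 1 step: not counted | 0.5: not counted |
| +1 | 2 steps: counted | 1.0: not counted |
| +2 or more | counted | counted |

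With the manual's grading, a new hypopyon, hyphema, anterior synechia, keratic precipitate or corneal infiltrate at +0.5 is omitted on both readings. At +1 it is omitted on the points reading. A new posterior synechia, being ungraded, counts whenever it appears. For cells, the +1 row decides whether a new 6 to 15 cells is reported.

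**Flare.** Take new flare at +1. On the manual's scale (0, 0.5, 1) it is two steps and counts by steps. On the SAP's scale (0, 1) it is one step and does not. By points it fails on both, so this discrepancy changes the result only under the steps reading. Separately, flare entered as +0.5 has no SAP category at all.

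**The case against.** **Adverse event reporting catches these changes.** Protocol 6.1 allows any unfavorable, unintended sign to be an adverse event and treats worsening of a pre-existing condition as one. SAP 10.2.3 tabulates ocular treatment-emergent events with no grade threshold, and Protocol 7.6 lists all adverse events by subject. A reader might infer from SAP 10.5.4 that the omitted changes are never tabulated anywhere. The documents do not support that. But nothing in them makes a slit-lamp grade change an adverse event automatically, so this route depends on the investigator and does not replace a summary of the examination.

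**High baselines should be rare.** Protocol 5.1 excludes ocular conditions that could affect safety (uveitis is an example), corneal abnormalities likely to interfere with acuity, severe dry eye, and abnormal ophthalmic findings in the investigator's judgment. Most eyes should start near 0, and from 0 every new moderate or severe finding counts on both readings. This stands. The counts above describe the rule and do not predict how often findings will be missed. The practical weight lies on new trace and new mild signs.

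**An eye at grade 2 is not always beyond reach.** A reader might infer that a moderate baseline can never produce a counted worsening. That is so on the 0 to 3 scale, but on the 0 to +4 scale a move from 2 to 4 counts on both readings.

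**Hypopyon and hyphema could be read as ungraded.** The SAP gives them no scale, so someone working from it alone could place them under the absence-to-presence route and count any new one. That is possible, but it conflicts with the manual's grading. It is a further reason to state the classification.

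**The threshold itself is a choice.** It is prespecified, applies equally to both arms, and limits noise from repeated subjective grading. A reader might infer that it is wrong and should be lowered. A rule of at least 1.0 point would count 8 of the 10 worsenings on the general scale, but nothing in the documents shows that to be the correct cut. A high threshold does not, however, explain the undefined unit, the two flare scales, or the lack of a listing.

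**Conclusion.** The point holds as a defect of definition and coverage in one safety table. Followed as written with the sites' grading, SAP 10.5.4 omits new hypopyon, hyphema, anterior synechiae, keratic precipitates and corneal infiltrates at +0.5 on either reading, and at +1 on the points reading. It omits every one-step worsening: 4 of 10 on the general scale and 5 of 15 on the manual's anterior chamber scale. The undefined unit changes the result for one transition, 0 to 1, which is the one that decides whether a new mild finding is reported. The flare scales conflict between the two documents.

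This rests on two assumptions: that the data are captured on the manual's scales (the case report form is not among the documents), and that the SAP's reference to findings without a severity grade follows the manual's division into graded and ungraded. How many subjects would be affected cannot be derived from the documents. The efficacy conclusions are not touched.

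**What to change.** In SAP 10.5.4:

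1. State whether a grade means one scale step or one point.
2. Extend the absence-to-presence route to any new hypopyon, hyphema, anterior synechiae, keratic precipitates or corneal infiltrates, at any grade.
3. Reconcile the flare scale with Operations Manual 3.18, and say how a +0.5 flare entry is handled.
4. Add a by-subject slit-lamp listing, or a shift table from baseline to worst post-baseline grade, so that one-step worsening is visible with the general threshold unchanged.

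This needs SAP wording (and a correction to the manual if the flare scale is settled that way), one programming rule and one more output. It needs no new examinations. The price is a few more low-grade findings in the table.

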10.5.5 Manifest Refraction

Both mesopic manifest refraction (distance and near) and photopic manifest refraction (distance and near) will be assessed in each eye at Screening. If a subject loses ≥ 1 line (≥ 5 letters) of CDVA or DCNVA compared with Hour 0 of the same study visit at Hour 1 after dosing, a manifest refraction should be repeated under the same lighting conditions.

Manifest refraction assessments will be listed.

10.5.6 Dilated Fundoscopic Examination

Dilated fundoscopic examination will be performed in each eye at Screening and at Hour 9 on Day 14/early exit.

Findings from dilated fundoscopic examination will be listed.

10.5.7 Post-Dose Tolerability

Post-dose tolerability will be assessed after each dose at each visit in all subjects who report any of the following ocular symptoms after drop instillation:

- blurred vision/vision disturbance
- foreign body sensation/grittiness
- pain
- burning/stinging/irritation
- tearing/watery eyes/discharge
- itching

These subjects will rate each of these symptoms using a 5-point scale (0 = none, 0.5 = trace, 1 = mild, 2 = moderate, and 3 = severe) for severity and a 3-point scale (< 1 min, 1 to 5 min, and > 5 min) for duration. The number and percentage of subjects who report each category of severity and duration will be tabulated for each time point by treatment group.

10.5.8 Drop Comfort

Drop comfort will be assessed in all subjects after each dose at each visit.

Subjects will rate the overall comfort of the treatment drops using a 6-point scale (soothing, very comfortable, comfortable, uncomfortable, very uncomfortable, and intolerable). The number and percentage of subjects who report each category will be tabulated for each time point by treatment group.

10.6 Safety Subgroup Analyses

Ocular TEAEs will be summarized by preferred term for each of the following subgroups:

- Age group (≤ 50 , > 50 years)

- Sex (male, female)
- Race (white, black or African American, Asian, American Indian or Alaska Native, Native Hawaiian or other Pacific Islander, and multiple.)
- Ethnicity (Hispanic or Latino, not Hispanic or Latino)

11.0 Other Analyses

Plasma concentrations of AGN-190584 will be assessed at selected sites in approximately 10% of all enrolled subjects. Details of the statistical analyses of PK data will be described in the PK analysis plan finalized before database lock.

Additional PRO exploratory analyses other those described in Section 9.5 will be described in a separate analysis plan (Appendix A).

12.0 Interim Analyses

Not applicable.

12.1 Data Monitoring Committee

Not applicable.

13.0 Overall Type-I Error Control

A fixed sequence testing procedure will be applied to control the overall familywise Type I error rate at $\alpha = 0.05$ for the primary and secondary hypotheses sequentially. The hypotheses for primary endpoint and the secondary endpoints will be tested in a sequential order:

- **H1 Primary:** The proportion of subjects gaining 3 lines or more in mesopic, high-contrast, binocular DCNVA with no more than 5-letter loss in mesopic CDVA with the same refractive correction at Day 14, Hour 9 (3 hours after the second dose)

- **H2: Key Secondary:** The proportion of subjects gaining 3 lines or more in photopic, high-contrast, binocular DCNVA with no more than 5-letter loss in photopic CDVA with the same refractive correction at Day 14, Hour 9 (3 hours after the second dose)
- **H3 Supportive Secondary:** The proportion of subjects gaining 2 lines or more in mesopic, high-contrast, binocular DCNVA with no more than 5-letter loss in mesopic CDVA with the same refractive correction at Day 14, Hour 9 (3 hours after the second dose)
- **H4 Supportive Secondary:** The proportion of subjects achieving 20/40 or better in mesopic, high-contrast, binocular DCNVA with no more than 5-letter loss in mesopic CDVA with the same refractive correction at Day 14, Hour 9 (3 hours after the second dose)

If the statistical test at any step fails, the test procedure will stop and no further hypotheses will be tested.

14.0 **Version History**

Table 3. SAP Version History Summary

Version	Date	Summary
1.0	19 NOV 2021	Original version

15.0 **References**

Appendix A. PRO Scoring Algorithm

The NVPTQ and the PICQ scoring algorithms can be found in:

- Scoring Algorithms for Presbyopia Patient-Reported Outcome Instruments
December 9, 2019 by Outcometrix

VFA app coping behavior metric scores and candidate composite scores can be found in:

- Psychometric Evaluation of the Visual Function Assessment Scores in
Presbyopia Final Psychometric Analysis Plan
June 17, 2021 by RTI Health Solutions

Appendix B. Definition of Adverse Events of Special Interest

AESIs will be identified using the following search criteria¹:

Area of Safety Interest	Search Criteria – Preferred Term (PT)	PT Code
Headache	Headache	10019211
	Migraine	10027599
	Migraine with aura	10027607
	Sinus headache	10040744
	Other PT(s) related to headache of special interest	(TBD)
Visual disturbance	Dyschromatopsia	10013892
	Glare	10052128
	Halo vision	10019099
	Metamorphopsia	10063341
	Photophobia	10034960
	Photopsia	10034962
	Pseudomyopia	10075919
	Vision blurred	10047513
	Visual acuity reduced	10047531
	Visual field defect	10047555
	Visual impairment	10047571
	Other PT(s) related to visual disturbance of special interest	(TBD)

1. The final list of PTs to be used will be reviewed and finalized prior to database lock.

Appendix C. List of MedDRA Preferred Terms for COVID-19 Infection

Area of Safety Interest	Search Criteria
COVID-19 Infection	MedDRA 24.1 COVID-19 SMQ 20000237 (narrow search)
